#### 16.1.2 Descriptive Statistics of PK Parameter Data

PK parameter data will be descriptively summarized using: number of subjects (N), number of non-missing observations (n), arithmetic mean (Mean), standard deviation (SD), coefficient of variation (CV%), minimum (Min), median (Median), maximum (Max), geometric mean (GeoMean), the geometric coefficient of variation (GeoCV) and the 95% confidence interval for the GeoMean (LCI 95% GM, UCI 95% GM). For PK parameters related to time (e.g.  $t_{max}$   $t_{last}$ ), only n, Min, Median, and Max may be reported.

Descriptive statistics will only be calculated for a PK parameter when n>2.

PK parameters read directly from the measurements (i.e.  $C_{max}$ ) will be reported with the same precision as the source data. All other PK parameters will be reported to 3 significant figures. In export datasets, as well as in the SDTM PP domain, PK parameters will be provided with full precision and will not be rounded. Descriptive statistics of PK parameter data will be calculated using full precision values and rounded for reporting purposes only.

The following conventions will be applied when reporting descriptive statistics of PK parameter data:

N, n	0 decimal place
Mean, Min, Median, Max, GeoMean, 95% CI:	3 significant digits
SD:	4 significant digits
CV%, GeoCV%:	1 decimal place

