### 16.1.3 Statistical Analysis of PK Parameter Data

Dose proportionality will be provided separately for  $AUC_{0-\infty}$ ,  $AUC_\tau$ ,  $AUC_{0-tlast}$  and  $C_{max}$  on study day 1 and 8 for Part 1A using a power model. The power model will have the form:

$$Y = a * (dose)^b$$

where Y is the PK parameter, and a and b are the coefficient and exponent, respectively, of the power equation. By taking the natural logarithm (ln), the power model can be analysed using linear regression and has the form:

$$\ln(Y) = \ln(a) + b * \ln(dose) + \text{error}$$

$$= \alpha + \beta * \ln(dose) + \text{error},$$

where  $\alpha$  is the intercept, and  $\beta$  is the slope, and  $\ln(dose)$  is based on the dose size for each subject. For each PK parameter, the point estimate of slope  $\beta$  and its 95% CI will be provided. In addition, the estimated regression line will be overlaid on the individual points in the corresponding scatter plot (log-log scale).

Dose proportionality will be declared if the 90% confidence interval (CI) for  $\beta$  is entirely contained within the critical region,

$$\left( 1 + \frac{\ln(0.50)}{\ln(r)}, 1 + \frac{\ln(2.00)}{\ln(r)} \right)$$

where  $r$  is the ratio of the highest and the lowest dose in a given part of the study. Dose proportionality for participants who were administered the study intervention will be tested for  $C_{max}$  and  $AUC_{0-\infty}$ ,  $AUC_\tau$ ,  $AUC_{0-tlast}$  on Day 1 and at steady state.

Since the study is neither optimally designed nor powered to confirm the presence or absence of meaningful departures from dose proportionality, these results should be interpreted with caution. In addition, graphical assessment would also be considered to understand dose proportionality.

If the samples remain above LLOQ for the whole dosing interval, then  $AUC_{0-t_{last}}$  will be the same as  $AUC_{\tau}$  for Part 1A as there is another dose after 24 hours

A statistical analysis will be conducted to investigate the food effect on the treatment by comparing (fed) treatment to (fasted) treatment for Part 1B.

The natural log (ln)-transformed  $AUC_{0-\infty}$ ,  $AUC_{\tau}$ ,  $AUC_{0-t_{last}}$  and  $C_{max}$  will be analyzed using a mixed effect model. The model will include planned treatment sequence, period, and actual treatment as fixed effects, and subject within planned treatment sequence as a random effect.

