#### **16.1.4 General Specifications for PK Concentration and PK Parameter Data**

Predose samples that occur before the first or subsequent drug administration will be assigned a time of 0 hours, as if the sample had been taken simultaneously with the study intervention administration.

Predose or trough samples which have been taken after the subsequent dosing will be reported as a protocol deviation. The resulting concentrations will be included in concentration listings but excluded from descriptive statistics of concentrations and from PK parameter estimation.

Values below the lower limit of quantification (BLQ) will be taken as zero for summary statistics of PK concentration data, PK parameter estimation (e.g. AUC) and for graphical presentations.

In case profiles have a measurable pre-dose concentration less than or equal to 5% of its  $C_{max}$  value, the participant's data will be included in the PK and statistical analyses without any adjustments. If the pre-dose value is greater than 5% of the  $C_{max}$ , the participant's data for the affected profile will be included in the PK evaluation but excluded from descriptive and further statistical evaluation after agreement with the sponsor.

Missing concentrations (e.g. no sample, insufficient sample volume for analysis, no result or result not valid) will be reported and used generally as "N.R.". A participant who withdraws prior to the last planned observation will be included in the analyses up to the time of discontinuation.

Samples that are collected outside with a time deviation of > 10% from the protocol-scheduled time will be included in the PK parameter estimation (NCA) but will be excluded from the concentration summary and mean/median concentration plots.

PK concentrations which are erroneous due to a sampling processing or analytical error (as documented in the bioanalytical report) may be excluded from the PK analysis if agreed by the Sponsor. In this case the rationale for exclusion will be provided in the CSR. Any other PK concentrations that appear implausible to the Clinical Pharmacologist/Clinical PK/PD Scientist will generally not be excluded from the analysis and data handling will be agreed with the sponsor clinical pharmacologist/PK scientist. Any implausible data will be documented in the CSR.

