### 16.1.5.1 Estimation of Pharmacokinetic Parameters in Plasma

PK parameters analysis will be calculated using the actual elapsed time since dosing, with the exception of the interim analysis for SMC. In cases where the actual sampling time is missing, calculations may be performed using the scheduled time. Details (e.g. number of samples, participants affected) will be described in the CSR. In cases actual dosing time is missing, scheduled time might be used for NCA after performance of adequate plausibility checks and agreement with the sponsor. Decision and rationale should be included in the CSR.

The following plasma PK parameters will be calculated for M4076 where appropriate

Symbol	Definition
AUC 0-tlast	The area under the concentration-time curve (AUC) from time zero (= dosing time) to the last sampling time ( $t_{last}$ ) at which the concentration is at or above the lower limit of quantification. Calculated using the mixed log-linear trapezoidal rule (linear up, log down).
AUC 0-tlast /Dose	The Dose normalized AUC from time zero to the last sampling time ( $t_{last}$ ) at which the concentration is at or above the lower limit of quantification. Normalized using the actual dose, using the formula $AUC_{0-t_{last}} / \text{Dose}$ .
AUC <math>\tau</math>	The AUC over the dosing interval from $T1=0$ h to $T2=\tau$ h. Calculated using the mixed log-linear trapezoidal rule (linear up, log down). For single dose, $AUC_{\tau}$ is calculated as a partial area with the defined time range. In multiple dose profiles $AUC_{\tau}$ is calculated at steady state from one pre-dose time point to the dosing interval time. In cases where the actual observation time is not equal to the scheduled observation time $AUC_{\tau}$ will be calculated based on the estimated concentration at $\tau$ hours, and not the concentration at the actual observation time where a regression has been performed.
AUC <math>\tau</math> /Dose	The dose normalized AUC over the interval from $T1=0$ h to $T2=\tau$ h. Normalized using actual dose, using the formula $AUC_{\tau} / \text{Dose}$ .

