AUC 0-72	The AUC from time zero (= dosing time) to 72 hours post-dose. Calculated using the mixed log-linear trapezoidal rule (linear up, log down). In cases where the actual observation time is not equal to the scheduled observation time (72 hours), $AUC_{0-72}$ will be calculated based on the estimated concentration at 72 hours, and not the concentration at the actual observation time (Part 1B only).
AUC 0-72 /Dose	The dose normalized AUC from time zero (= dosing time) to 72 hours post-dose. Normalized using actual dose, using the formula $AUC_{0-72} / \text{Dose}$ . (Part 1B only)
AUC 0-<math>\infty</math>	The AUC from time zero (dosing time) extrapolated to infinity, based on the predicted value for the concentration at $t_{last}$ , as estimated using the linear regression from $\lambda_z$ determination. $AUC_{0-\infty} = AUC_{0-t_{last}} + C_{last \text{ pred}} / \lambda_z$ (single dose only)
AUC 0-<math>\infty</math> /Dose	The dose normalized AUC from time zero extrapolated to infinity. Normalized using actual dose, using the formula $AUC_{0-\infty} / \text{Dose}$ . (single dose only)
CL/F	The apparent total body clearance of study intervention following extravascular administration. $CL/F = \text{Dose p.o.} / AUC_{0-\infty}$ . (single dose)
C max	Maximum observed concentration
C max /Dose	The dose normalized maximum concentration. Normalized using the actual dose, and the formula $C_{max} / \text{Dose}$ .
C trough	The concentration observed immediately before next dosing (Part 1A only)
LI	The linearity index after repeated administration calculated as $LI = (AUC_{\tau} \text{ after multiple dose}) / (AUC_{0-\infty} \text{ after single dose})$ (Part 1A, Day 8 only)
R acc(AUC<math>\tau</math>)	The accumulation ratio after repeated administration calculated as $R_{acc}(AUC_{\tau}) = (AUC_{\tau} \text{ after multiple dose}) / (AUC_{\tau} \text{ after single dose})$ (Part 1A, Day 8 only)
R acc(Cmax)	The accumulation factor to assess the increase in maximum concentration until steady state is reached. $R_{acc}(C_{max}) = (C_{max} \text{ after multiple dose}) / (C_{max} \text{ after single dose})$ (Part 1A, Day 8 only)
t 1/2	Apparent terminal half-life. $t_{1/2} = \ln(2) / \lambda_z$
t last	The last sampling time at which the concentration is at or above the lower limit of quantification

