- In cases BLQ concentrations occur at the end of the collection interval, these concentrations might be set to missing for calculations of partial AUCs. This is an exemption to the general BLQ handling rule and should be applied in case its application would result in estimation of implausible partial AUC values. Implausibility is considered in cases partial AUCs were greater than  $AUC_{0-\infty}$ .
- At steady state, the pre-dose concentration may be duplicated and used as the trough concentration for calculation of  $AUC_\tau$  if the sample prior to the next dose is missing and vice versa.

The following PK parameters will be calculated for diagnostic purposes and listed, but will not be summarized:

Symbol	Definition
$\lambda_z$ low	First ( $\lambda_z$ low) time point of the time interval of the log-linear regression to determine $\lambda_z$ .
$\lambda_z$ up	Last ( $\lambda_z$ up) time point of the time interval of the log-linear regression to determine $\lambda_z$ .
$N\lambda$	Number of data points ( $N\lambda$ ) included in the log-linear regression analysis to determine $\lambda_z$ .
Rsq, adj	Adjusted goodness of fit statistic (adjusted Rsq) for calculation of $\lambda_z$
AUC extra%	AUC from time $t_{last}$ extrapolated to infinity given as percentage of AUC 0-∞ . (AUC extra% )
Span ratio	Span ratio of interval over which $t_{1/2}$ was estimated/ $t_{1/2}$

The regression analysis should contain data from at least 3 different time points in the terminal phase consistent with the assessment of a straight line on the log-transformed scale. Phoenix WinNonlin “best fit” methodology will be used as standard. If warranted, further adjustment may be made by the pharmacokineticist, after agreement with the Sponsor. The last quantifiable concentration  $>LLOQ$  should always be included in the regression analysis, while the concentration at  $t_{max}$  and any concentrations BLQ which occur after the last quantifiable data point  $>LLOQ$  should not be used.

If AUCextra%>20% and/or the coefficient of correlation (Rsq adj) of  $\lambda_z$  is <0.8 and/or the observation period over which the regression line is estimated (span ratio) is less than 2-fold the resulting  $t_{1/2}$ , the rate constants and all derived parameters (e.g.  $t_{1/2}$ , AUC0-∞, CL/F etc.) will be listed, flagged and included in the parameter outputs and excluded from descriptive statistics and further statistical evaluation.

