### 16.1.6.1 Listings and Tables

The following PK tables will be produced (PK Analysis Set):

Part 1A + Part 1B (Day 4 predose onwards)

- Descriptive statistics of concentrations of M4076 in plasma by part, day, and dose level
- Descriptive statistics of plasma PK parameters for M4076 by part, day, and dose level (do not include diagnostic parameters).
- Descriptive statistics of dose normalized plasma PK parameters for M4076 by part, day and dose level.
- Descriptive statistics of plasma trough concentrations (Ctrough) by part and dose level, using standard descriptive statistics for Days 2, 8, 9, 22 and predose samples for subsequent cycles

Part 1B (Food effect assessment period up to Day 4 predose)

- Descriptive statistics of concentrations of M4076 in plasma by dietary status
- Descriptive statistics of plasma PK parameters and CLR for M4076 by dietary status (do not include diagnostic parameters).
- Descriptive statistics of dose normalized plasma PK parameters for M4076 by dietary status
- Descriptive statistics of amount and fraction excreted in urine by interval and cumulatively by dietary status.

The following PK Listings will be produced (Safety Analysis Set):

Part 1A + Part 1B (Day 4 predose onwards)

- Individual plasma concentrations of M4076 by part, day and dose level
- Individual plasma PK parameters for M4076 by part, day and dose level
- Individual dose normalized plasma PK parameters for M4076 by part, day and dose level
- Trough plasma concentrations (Ctrough) of M4076 by part and dose level, Days 2, 8, 9, 22 and predose samples for subsequent cycles.
- Plasma PK diagnostic parameters for M4076 by part, day and dose level
- Plasma M4076 PK sampling date, actual time, nominal time, deviation from time, percentage time deviation, concentration by participant, part and dose level status sorted in chronological order

Part 1B (Food effect assessment period up to Day 4 predose)

- Individual plasma concentrations of M4076 by dietary status
- Individual urine concentrations of M4076 by dietary status
- Individual plasma PK parameters and CLR (Part 1B) for M4076 by dietary status
- Individual dose normalized plasma PK parameters for M4076 by dietary status.
- Individual amount and fraction excreted in urine, by interval and cumulatively and dietary status.
- Plasma PK diagnostic parameters for M4076 by dietary status.

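### The 5%-of-Cmax pre-dose exclusion in SAP 16.1.4 is not limited to profiles with an expected pre-dose value of about zero, so as written it reaches Part 1A Day 8 profiles

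*SAP*

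**What the plan says.** SAP 16.1.4 sets general rules for all PK data. A profile with a measurable pre-dose value up to 5% of its Cmax is used without adjustment. Above 5%, the participant's data for that profile are "included in the PK evaluation but excluded from descriptive and further statistical evaluation after agreement with the sponsor". The rule names no part, day or type of dosing. The same section uses the term predose for later doses as well as the first: "Predose samples that occur before the first or subsequent drug administration will be assigned a time of 0 hours".

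Other parts of the SAP plan to analyse Day 8 of Part 1A, which is a multiple-dose profile:

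- Section 16.1.3 assesses dose proportionality "on study day 1 and 8 for Part 1A using a power model".
- Section 16.1.6.1 tabulates plasma PK parameters by day and dose level, and summarises trough concentrations "using standard descriptive statistics for Days 2, 8, 9, 22 and predose samples for subsequent cycles".
- Section 16.1.5.1 defines the accumulation ratios and the linearity index for "Part 1A, Day 8 only".
- Section 16.1.5.1 says that AUCtau in multiple-dose profiles "is calculated at steady state from one pre-dose time point to the dosing interval time". It adds: "At steady state, the pre-dose concentration may be duplicated and used as the trough concentration for calculation of" AUCtau.

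Section 16.1.2 sets a minimum count: "Descriptive statistics will only be calculated for a PK parameter when n>2".

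**The concern.** A 5% pre-dose rule guards against carryover in a profile that should start from about zero. That fits the first dose in Part 1A and the two single-dose periods of the Part 1B crossover. It does not fit Day 8. Part 1A is dosed once daily (Protocol Table 8), so the Day 8 pre-dose sample is the trough left by seven earlier doses. A high value there reflects ordinary accumulation.

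PK after multiple doses is part of a secondary objective. If the rule is followed as written, valid Day 8 profiles drop out of the summaries of AUCtau, Cmax, accumulation ratios, linearity index and Day 8 trough, out of the mean and median figures, and out of the Day 8 power model. The trigger is the trough-to-peak ratio, so the profiles lost would tend to be those of participants who eliminate the drug more slowly.

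**Working it through.** The plan gives no figure to reproduce here, because 5% is a data-handling threshold. The check has three parts.

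**1. Scope of the text.** Section 16.1.5.1 limits its rules where it means to: certain parameters apply to single dose only, Part 1B only or Part 1A Day 8 only, and the trough substitution applies at steady state. The 5% rule has no such limit, and no available section exempts Day 8. A distinction between pre-dose and trough does not help. Section 16.1.4 uses predose for samples before later doses, and section 16.1.5.1 uses pre-dose for steady state.

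**2. Would Day 8 profiles cross 5%?**

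Inputs from the documents: a dosing interval of 24 h, seven doses before Day 8, and Day 8 post-dose samples at 1, 2, 3, 4, 6 and 8 h (Protocol Table 3). Half-life and absorption rate are not given. They are assumed: ka of 0.5, 1 and 2 per h, with half-life varied.

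- One-dose curve, up to a scale factor: c(t) = ka/(ka − k) × [exp(−kt) − exp(−ka·t)], with k = ln 2 / half-life.
- Day 8 pre-dose: the sum of c(24i) for i = 1 to 7.
- Day 8 Cmax: the largest value, over the pre-dose and sampling times, of the sum of c(t + 24i) for i = 0 to 7.
- Example, half-life 8 h and ka 1 per h: 0.156 / 0.910 = 17.2%.
- Half-life at which the ratio equals 5%: 4.23, 4.78 and 5.05 h for ka 0.5, 1 and 2 per h. With instantaneous absorption it is 24 × ln 2 / ln 20 = 5.55 h.

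The share of profiles above 5% was then simulated with lognormal variability. Eight assumed sets were used: SD of clearance 0.2 to 0.5, of volume 0 to 0.5 and of ka 0 to 0.4, with clearance–volume correlation 0 or 0.8. Ranges run over the eight sets and three ka values.

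| Assumed half-life | Typical Day 8 pre-dose/Cmax | Share of Day 8 profiles above 5% |
|---|---|---|
| 2 h | below 0.2% | 0–16% |
| 3 h | 0.6–1.4% | 0.3–33% |
| 5 h | 4.8–8.1% | 47–81% |
| 8 h | 15–21% | 74–99.9% |
| 12 h | 28–36% | 89% or more |

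At 5 h, the retained profiles have a geometric mean half-life of 0.51 to 0.87 of the full-group value, shorter in every set. Their geometric mean AUC is 0.65 to 1.03 of the full-group value, so the direction of any effect on AUC is not fixed.

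**3. Small cohorts.** The planned cohort size is about 3 (Protocol 9.2). One exclusion leaves 3 − 1 = 2, which fails n>2, so that cohort has no Day 8 parameter summary. The MTD and/or RDE level needs at least 6 participants (Protocol 4.1.1) and is less exposed.

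**The case against.** **The rule conflicts with less than it may seem.** A reader might infer that it contradicts the definitions of AUCtau, the accumulation ratios and the linearity index, or the use of a steady-state pre-dose value as a trough. It does not. Affected profiles stay in the PK evaluation, so the parameters are still estimated and listed. Those sections only show that the SAP treats a steady-state pre-dose value as valid data. What the rule can remove is the Day 8 summaries, figures and power model. This objection stands.

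**The wider scope is probably unintended, and there are safeguards.** Exclusion needs sponsor agreement, excluded values are listed and flagged with a reason in the study report, and a data review meeting precedes database lock. So the loss is conditional and would not be silent. But the SAP gives no criterion for agreement, which leaves the choice until after the data are seen, and none of these steps narrows the rule.

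**The size is unknown.** Without a half-life the affected share runs from none to nearly all. Some loss at long half-lives also has another cause. At 12 h, a 24 h Day 1 profile in the same model has about 26 to 28% of AUC extrapolated. That exceeds the 20% limit in 16.1.5.1, so the linearity index would largely be lost anyway. AUCtau and Cmax are not affected in that way.

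**The cohort of 3 is the lower edge.** Planning 22 to 28 participants over 4 levels averages 22/4 = 5.5 to 28/4 = 7 per level, and any other missing profile in a cohort of 3 has the same effect. This is fair, and the example should be read as a lower edge.

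**Biased exposure or dose choice.** A reader might infer that the rule biases AUC in a known direction or distorts selection of the recommended dose. The documents do not support either. The AUC ratio falls on both sides of 1, and committee analyses follow a separate plan (SAP 6.1).

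**Conclusion.** The point holds as a fault of scope: the rule as stated is broader than its purpose and reaches Part 1A Day 8 profiles that the SAP plans to analyse. It undercuts the Day 8 descriptive summaries and power model but not parameter estimation. Under the assumed model it matters little at a half-life of about 2 h, begins to catch typical profiles at about 4.2 to 5.1 h, and covers most Day 8 profiles at 8 h or more. These figures rest on assumed absorption, half-life and variability, and on the sponsor agreeing to exclusions. The study is exploratory, and section 16.1.3 already asks for caution with the power model, so the consequence is limited. The change should still be made, because it is nearly free and removes a decision otherwise left until the data are in hand.

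**What to change.** Add to SAP 16.1.4:

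- The 5% rule applies only to the Part 1A first-dose profile and to the two Part 1B food-effect profiles (single doses on Day -7 and Day 1).
- It does not apply to Part 1A multiple-dose profiles, meaning Day 8 or the day to which Day 8 sampling is moved under the Protocol Table 3 footnote, or to later multiple-dose profiles in Part 1B.
- Handling of Part 1B Day 4 is stated separately. It should not be labelled steady state, because its pre-dose sample is the 72 h residual of the Day 1 single dose. In the same model that residual is about 4 to 5% of Cmax at a 15 h half-life and 7 to 8% at 18 h.

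The crossover keeps its protection against carryover. A washout of five half-lives leaves 1/2^5 = 3.1% of the starting concentration, and seven days at a half-life of 28.8 h leave 2^(−168/28.8) = 1.8%. The 28.8 h comes from dividing the 6-day upper limit on the adjustable washout by five (144/5). It is an assumed value, not a measured one.

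The cost is a few lines of SAP text, with no new data or analyses.

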Plasma – Circulating Tumor DNA Sample		X									Collect predose.
Fresh Paired Tumor Biopsies	X									X	Mandatory collection, if not contraindicated for medical reasons. The first of two paired biopsies must be collected anytime during screening. The second biopsy must be collected on D4 from 2 to 4 hours after study intervention. No bone biopsies are allowed.
Blood - Immune Phenotyping		X									Collect predose.
Serum/plasma – Circulating Factors		X									Collect predose.

AE = adverse event; aPTT = activated partial thromboplastin time; CT = computed tomography; D = Day; DNA = deoxyribonucleic acid; ECG = electrocardiogram; ECOG = Eastern Cooperative Oncology Group; HIV = human immunodeficiency virus; INR = international normalized ratio; MRI = magnetic resonance imaging; Pd = pharmacodynamic; PK = pharmacokinetic; PT = prothrombin time; RDE = recommended dose for expansion; SAE = serious adverse event; WOCBP = woman of childbearing potential.

1.3.3

Parts 1A and 1B – Pharmacokinetic, ECG, and Schedule

CCI

ampling

Table 3

Part 1A M4076 Monotherapy Dose Escalation: Pharmacokinetic, ECG and Assessments

CCI

Study Day	M4076 Dosing	PK Sampling Time	ECG ^b	Paired Biopsies	CCI
Screening (D -28 to -1)				X	
Day 1	X	Predose ^a	X		
		0.5 hour ± 10 minutes postdose			
		1 hour ± 10 minutes postdose			
		2 hours ± 10 minutes postdose	X		
		3 hours ± 20 minutes postdose	X		
		4 hours ± 20 minutes postdose	X		
		6 hours ± 20 minutes postdose	X		
Day 2	X	Predose ^a	X		
		2 hours -4 hours postdose ^c		X ^c	
Day 8	X	Predose ^a	X		
		1 hour ± 10 minutes postdose	X		
		2 hours ± 10 minutes postdose	X		
		3 hours ± 20 minutes postdose	X		

Study Day	M4076 Dosing	PK Sampling Time	ECG ^b	Paired Biopsies	CCl [REDACTED]
		4 hours ± 20 minutes postdose	X		
		6 hours ± 20 minutes postdose			
		8 hours ± 20 minutes postdose	X		
Day 9	X	Predose ^a			
Day 22	X	Predose ^a			X
		2 hours ± 10 minutes postdose			X
		4 hours ± 20 minutes postdose			X
All subsequent Day 1 of every 3 week treatment period	X	Predose ^a			

Note: The fasting window in Part 1A is defined as: 2 hours predose to 1-hour postdose in general, and 2 hours predose to 4 hours postdose on days where PK-time matched triplicate ECG will be collected.

ECG = electrocardiogram; γ-H2AX = gamma histone family member X; CCl [REDACTED]; PK = pharmacokinetic.

^a All predose samples have a window of -60 minutes prior to dosing.

^b The window period for ECG is the same as noted for PK sampling.

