^c Efforts should be made to collect blood for PK and CCl [REDACTED] and biopsy samples around similar time points (± 20 minutes).

Cl

Period 1 Day 8/9 PK sampling may be conducted on Day 15/16, or Period 2 Day 1/2, if required for logistical reasons and/or in case study intervention was interrupted and resumed. In this case, timing of associated triplicate ECG measurements should be rescheduled accordingly, and the Sponsor notified in advance.

Table 4

Part 1B Preliminary Food Effect Assessment: Pharmacokinetic, ECG and CCI Assessments

Study Day	M4076 Dosing	PK Sampling Time	Urine Collection for PK	ECG ^b	Paired Biopsies	CCI
Screening (D -28 to -8)					X	
-7	X	Predose ^a	X (1 hour, 0)	X		
		0.5 hour ± 10 minutes postdose	X (0 to 4 hours)			
		1 hour ± 10 minutes postdose		X		
		2 hours ± 10 minutes postdose		X		
		3 hours ± 20 minutes postdose		X		
		4 hours ± 20 minutes postdose	X (4 to 8 hours)	X		
		6 hours ± 20 minutes postdose		X		
		8 hours ± 20 minutes postdose	X (8 to 24 hours)	X		
		10 hours ± 20 minutes postdose				
-6		24 hours ± 2 hours postdose	X (24 to 48 hours)			
-5		48 hours ± 2 hours postdose	X (48 to 72 hours)			
-4		72 hours ± 2 hours postdose				
Day -3 to -1 Washout						

Study Day	M4076 Dosing	PK Sampling Time	Urine Collection for PK	ECG ^b	Paired Biopsies	CCI
Day 1	X	Predose ^a		X		
		0.5 hour ± 10 minutes postdose	X (0 to 4 hours)			
		1 hour ± 10 minutes postdose				
		2 hours ± 10 minutes postdose		X		
		3 hours ± 20 minutes postdose		X		
		4 hours ± 20 minutes postdose	X (4 to 8 hours)	X		
		6 hours ± 20 minutes postdose		X		
		8 hours ± 20 minutes postdose	X (8 to 24 hours)	X		
		10 hours ± 20 minutes postdose				
Day 2		24 hours ± 2 hours postdose	X (24 to 48 hours)			
Day 3		48 hours ± 2 hours postdose	X (48 to 72 hours)			
Day 4 ^d	X	Predose ^a				
		1 hours ± 10 minutes postdose				
		3 hours ± 60 minutes postdose			X ^c	
		6 hours ± 20 minutes postdose				
		8 hours ± 20 minutes postdose				

ECG = electrocardiogram; γ-H2AX = gamma histone family member X; Pd = pharmacodynamic; PK = pharmacokinetic; RDE = recommended dose for evaluation.

^a All predose samples have a window of – 60 minutes prior to next dosing.

- d** Triplicate ECG collection is only applicable to participants dosed in the fasted state. The fasting window in Part 1B is defined as 10 hours predose to 4 hours postdose.

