#### 16.1.1 Descriptive Statistics of PK Concentration Data

Plasma PK measurements will be listed and descriptively summarized using: number of subjects (N), number of non-missing observations (n), arithmetic mean (Mean), standard deviation (SD), coefficient of variation (CV%), minimum (Min), median (Median) and maximum (Max).

Missing statistics, e.g. when they cannot be calculated, should be presented as “NC”. “ND” will be used if a PK sample was not taken.

Descriptive statistics will only be calculated for n>2 in which a measurement of BLQ represents a valid measurement and will be taken as zero for summary statistics of PK concentration data. Values below the LLOQ will be treated as zero for the calculation of summary statistics and graphical presentations

Descriptive statistics of PK concentration data will be calculated using values with the same precision as the source data and rounded for reporting purposes only. In export datasets, as well as in the SDTM PC domain, PK concentrations will be provided with full precision and will not be rounded.

The following conventions will be applied when reporting descriptive statistics of PK concentration data:

N, n	0 decimal place
Mean, Min, Median, Max:	3 significant digits
SD:	4 significant digits
CV%:	1 decimal place

Urine concentrations and volumes will be listed but not be summarized.

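### The 10% timing rule in SAP 16.1.4 is tighter than the protocol's own sampling windows at 0.5 h, 1 h and, marginally, 3 h (and at 3 h on Part 1B Day 4), so compliant PK samples can drop out of the concentration tables and mean/median plots

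*SAP*

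**What the plan says.** SAP 16.1.4 deals with samples "with a time deviation of > 10% from the protocol-scheduled time". They "will be included in the PK parameter estimation (NCA) but will be excluded from the concentration summary and mean/median concentration plots". The SAP sentence is incomplete: something is missing after the word *outside*, so the percentage is the only criterion that can be applied.

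Protocol Section 1.3.3, Tables 3 and 4, sets the windows. The relevant ones are "0.5 hour ± 10 minutes postdose", "1 hour ± 10 minutes postdose", "2 hours ± 10 minutes postdose" and "3 hours ± 20 minutes postdose". Table 4 adds "3 hours ± 60 minutes postdose" on Part 1B Day 4. Table 3 also has a Part 1A Day 2 sample that may fall anywhere from 2 to 4 h after dosing, with no single nominal time.

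Two further rules decide what an exclusion does. For the concentration tables, SAP 16.1.1 states: "Descriptive statistics will only be calculated for n>2". For mean/median plots, SAP 16.1.4 needs only two values and shows individual data below that. Protocol Section 1.2 plans 3 participants per dose level in Part 1A.

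**The concern.** A site that follows the protocol exactly can still have its sample left out of the nominal-time summary. A percentage limit is tightest, in minutes, at the earliest times, so the loss falls mainly on 0.5 h and 1 h, in the absorption phase. Those rows and plotted points help describe the PK profile, a secondary objective. In Part 1B they also show how the fed and fasted curves differ early on. At a dose level with 3 participants, one exclusion leaves n=2 and the table row is not calculated.

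For the Part 1A Day 2 sample the rule cannot be applied at all, because there is no scheduled time from which to measure 10%.

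**Working it through.** The plan states no figure on this point, so there is none to reproduce.

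**Inputs.** Nominal time *t* and window *w*: Protocol 1.3.3, Tables 3 and 4. The 10% limit and the two-value plot rule: SAP 16.1.4. The n>2 rule: SAP 16.1.1. Cohort of 3: Protocol 1.2. At least 6 at the MTD/RDE: Protocol 4.1.1. Twelve in Part 1B: Protocol 9.2.

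**Step 1: compare the limits.** Largest compliant deviation = 100 × *w*/*t*. SAP tolerance = 0.10 × *t*.

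| Sample | Protocol window | Largest compliant deviation | SAP tolerance |
|---|---|---|---|
| 0.5 h | ±10 min | 10/30 = 33.3% | ±3 min |
| 1 h | ±10 min | 10/60 = 16.7% | ±6 min |
| 2 h | ±10 min | 10/120 = 8.3% | ±12 min |
| 3 h | ±20 min | 20/180 = 11.1% | ±18 min |
| 4 h | ±20 min | 20/240 = 8.3% | ±24 min |
| 3 h, Part 1B Day 4 | ±60 min | 60/180 = 33.3% | ±18 min |

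The later times in Tables 3 and 4 are all inside 10%: 6 h 5.6%, 8 h 4.2%, 10 h 3.3%, 24 h 8.3%, 48 h 4.2%, 72 h 2.8%. The alternative schedules in Protocol Appendix 7 have a 24 h ±4 h sample (16.7%), which matters only if one of them is adopted.

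**Step 2: share *p* of compliant samples dropped.** The timing distribution is an assumption, so three are used.

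- Uniform over the window: *p* = 1 − 0.10*t*/*w*. At 0.5 h, 1 − 3/10 = 0.70; at 1 h, 1 − 6/10 = 0.40; at 3 h, 1 − 18/20 = 0.10.
- Normal, truncated at a window of *k* SD (*k* = 2 or 3): *p* = 1 − [2Φ(*k* × 0.10*t*/*w*) − 1] / [2Φ(*k*) − 1]. At 0.5 h with *k* = 3, the first argument is 3 × 0.3 = 0.9 and *p* = 0.366.

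**Step 3: a dose level of 3, samples independent.** The table row is lost if any sample is dropped: 1 − (1 − *p*)³. Fewer than two values remain for the plot with probability *p*³ + 3*p*²(1 − *p*).

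| Quantity | Uniform | Window = 2 SD | Window = 3 SD |
|---|---|---|---|
| Dropped, 0.5 h | 70% | 53% | 37% |
| Dropped, 1 h | 40% | 19% | 7% |
| Dropped, 3 h ±20 min | 10% | 2.8% | 0.4% |
| Row lost, 0.5 h | 97% | 89% | 75% |
| Row lost, 1 h | 78% | 48% | 19% |
| Row lost, 3 h ±20 min | 27% | 8% | 1% |
| Fewer than 2 left for plot, 0.5 h | 78% | 54% | 30% |
| Fewer than 2 left for plot, 1 h | 35% | 10% | 1% |

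The Part 1B Day 4 3 h sample has the same drop rates as 0.5 h, because 18/60 = 3/10.

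**Step 4: larger groups, uniform timing.** With 6 participants the row is lost if 4 or more are dropped: 74% at 0.5 h, 18% at 1 h. With 12 per dietary state it is lost if 10 or more are dropped: 25% at 0.5 h, 0.3% at 1 h. At 0.5 h about 12 × 0.30 = 3.6 values per dietary state would remain on average.

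**Step 5: under the fix.** A compliant sample lies inside its window, so *p* = 0 at every fixed nominal time with an ordinary window. A fully compliant level of 3 keeps n = 3 and every row.

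**The case against.** The strongest reply is that a sampling window and an averaging tolerance do different jobs. The window defines compliance; the tolerance decides which values may be averaged under one label. A stricter tolerance where concentrations change fastest could be deliberate. In principle that is right, and it counts for the Part 1B Day 4 sample: pooling draws from 2 to 4 h as a 3 h mean would mislead. But the SAP gives no such rationale, and a limit of ±3 min at 0.5 h sets aside samples that the protocol treats as on time.

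A second reply is that the incomplete sentence may have meant samples outside the window *and* more than 10% off, in which case no compliant sample is lost. That is possible, but the text does not say it. The planned listings report percentage time deviation (SAP 16.1.6.1), so a programmer could apply the sentence literally.

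Third, the tables are by dose level, not cohort. Protocol 9.2 plans 22 to 28 participants over 4 levels, an average of 5.5 to 7. This stands: the figures for 3 apply only to levels that are not expanded.

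A reader might infer more than the documents support:

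- *Data are discarded.* They are not. The samples stay in the NCA on actual times, are listed and flagged, and appear in individual actual-time plots (SAP 16.1.4, 16.1.5.1, 16.1.6.2).
- *The food-effect result is weakened.* The fed/fasted ratios come from NCA parameters in a mixed model (SAP 16.1.3). The Day 4 3 h sample falls after the food-effect period, which ends at Day 4 pre-dose (SAP Section 9).
- *The SMC sees thinned profiles.* SMC analyses follow a separate plan (SAP 6.1), whose text is not available here, so no effect is shown.
- *Mean plots lose the time point whenever the table does.* They need only two values, so they are thinned and not always emptied.

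**Conclusion.** The point holds, with a limited scope. Read literally, SAP 16.1.4 is stricter than the protocol at 0.5 h, 1 h, marginally at 3 h, and at 3 h on Part 1B Day 4, and it excludes compliant samples from descriptive tables and mean/median plots at those times. The loss is per time point and depends on at least one sample being more than 10% off.

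For an unexpanded level of 3, losing the 0.5 h row is likely under all three timing assumptions. At 1 h the answer depends heavily on the assumption, and at 3 h ±20 min the effect is small. These assumptions are illustrations, not bounds: sites that draw within 3 minutes of nominal time would lose nothing. No primary endpoint, PK parameter, dose-proportionality result or food-effect estimate changes. The sentence should be corrected because it is incomplete and the remedy is small.

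**What to change.** Complete the sentence in SAP 16.1.4 so that a sample is left out of nominal-time concentration summaries and mean/median plots only if it is both outside the protocol window for that time point and more than 10% off nominal time. Keep actual times for the NCA and individual plots, as now.

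Add one line for the wide-window samples (Part 1B Day 4 at 3 h ±60 min and Part 1A Day 2 at 2 to 4 h): present them by actual time or in listings, and do not average them under one nominal time.

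The cost is a short SAP edit and slightly more timing scatter in the mean profiles at 0.5 to 1 h, where samples from 20 to 40 min and from 50 to 70 min would be averaged under their nominal times.
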